Title: Efficacy of the Quell Wearable Device for Fibromyalgia

NCT# 03714425

Date: 09/27/2018

RESEARCH DESIGN AND METHODS

We will recruit 100 patients (see the power analysis) with a primary complaint of FM and randomize each of the subjects to one of two treatment conditions: 1) the regular Quell device, and 2) a Minimal Frequency Quell device (control). All participants will be adults age 21 or older and diagnosed with FM. Patients will be invited to participate if they own a smartphone (iPhone or Android device) and can download the pain app and the Quell Relief program app onto their device. Patients will also be included if they (1) have chronic pain related to FM for > 3 months' duration, (2) average 4 or greater on a pain intensity scale of 0 to 10, and (3) are able to speak and understand English. A subject will need to meet the criteria set out by Wolfe et al., for fibromyalgia to be considered for inclusion in this trial: (1) wide spread pain, (2) pain for 3 months or longer, and (3) pain that is not accounted for by any other medical condition (see Table 2). We will also require that the participants have a "physician diagnosis" of fibromyalgia, meaning that they have been told that they have fibromyalgia and the diagnosis was entered in a medical record somewhere.

Patients will be excluded from participation if they meet any of the following criteria: (1) diagnosis of cancer or any other malignant disease, (2) acute osteomyelitis or acute bone disease, (3) present or past DSM-V diagnosis of schizophrenia, delusional disorder, psychotic disorder, or dissociative disorder that would be judged to interfere with study participation, (4) pregnancy, (5) any clinically unstable systemic illness judged to interfere with treatment, (6) a pain condition requiring urgent surgery, (7) an active substance use disorder, such as cocaine or IV heroin use (positive on the Mini International Neuropsychiatric Interview; M.I.N.I. v.5.0), that would interfere with study participation, and (8) have an implanted cardiac pacemaker, defibrillator, or other implanted device. All subjects will be asked to not change their treatment during the study period.

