All subjects (High Frequency Quell and Minimal Frequency Quell condition) will be encouraged to use their device for at least 2 therapy sessions (2 hours of stimulation) every day, and to wear the device as often as possible. Tracking of use of the device will be available electronically through the NeuroMetrix Quell app. All demographic and daily pain assessment data will be stored on a secure server (Veracode tested) at BWH and messages will be sent via the 2-way messaging pain app program to help track use of the device. Patients who wish to discontinue the study will be allowed to do so at their request. If the participant is willing, we will meet with her or him to understand reasons for discontinuing the study and problem-solve to see if there is a way to keep following the individual. All subjects will be asked to complete a packet of mailed mid-point assessments approximately 6 weeks after the start of the study and return the completed assessments in pre-addressed stamped envelopes. All subjects will also be asked to complete post-intervention mailed assessments after 3 months. Each subject will be compensated \$25 at baseline and \$50 at study completion upon receipt of their completed questionnaires. All subjects will be allowed to keep their Quell device at the end of the study. Those subjects assigned to the Minimal Frequency Quell condition will be offered to switch to a High Frequency Quell at the end of the 3-month trial period. It is expected that 15% of the subjects will dropout before completing the study and recruitment of 115 subjects will be needed.

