Patient Measures: We will be tracking the patients using validated measures of pain (The Brief Pain Inventory - BPI), fibromyalgia (Revised Fibromyalgia Impact Questionnaire – FIQR), coping (Pain Catastrophizing Scale - PCS), level of disability (Pain Disability Index - PDI), mood (Hospital Anxiety and Depression Scale - HADS), presence of neuropathy (Pain Detect Neuropathic Pain Questionnaire – painDETECT), impression of change (Patients' Global Impression of Change – PGIC), healthcare utilization (monthly clinic and ED visits), and overall satisfaction (Satisfaction and qualitative questions developed for this study specifically related to use of a pain management device; see Table 1). We will also track daily ratings of pain, sleep, activity interference, and mood through the pain app. Objective measures of activity, gait, and sleep will be collected by the devices.

Research Objectives: This study is expected to take 18 months to complete and is designed to gather information about the use of the Quell for persons with chronic fibromyalgia-related pain. We hypothesize that those assigned to using the High Frequency Quell device will report reduced pain compared with those in the Minimal Frequency Quell condition; with those using the High Frequency device also showing improvement in sleep, mood, and level of activity. We hypothesize that frequency of using the Quell (increased tolerability and adherence) will be correlated with greater reduction in pain. We hypothesize that the device will be safe to use and will demonstrate a reduction in healthcare utilization (reduced clinic and ED visits). We will also investigate use of prescription opioids and other nonopioid pain medications among the study subjects and determine the effect of daily use of the High Frequency Quell (vs. Minimal Frequency Quell) on intake of prescription pain medication. Finally, based on preliminary analyses limited by few subject numbers, we will investigate whether certain individuals report greater benefit from using the Quell than others and, in particular, we predict that those with more sensitivity and longer duration of pain will demonstrate most benefit. We will target the PGIC as the primary outcome measure, since it gives a global impression of change in pain, activity limitation, emotions, and overall quality of life. We will target the BPI, FIQR, PCS, PDI, HADS, healthcare utilization, and satisfaction questions as secondary outcome measures.

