Power Analyses: Power calculations, as outlined by Cohen (1988), were performed to determine the probability of detecting clinically significant differences between treatment groups in the primary area of measurement: Patients' Global Impression of Change – (PGIC). These calculations assumed a two-tailed test and alpha level of 0.05 confirming the hypotheses that

the Quell would be associated with general overall improvement (e.g., more pain relief, less emotional distress, and less activity interference). In our previous work (Jamison, Wan et al, submitted), we had a high rate of consent to participate among recruited patients, without any significant attrition. We assessed power using a range of plausible parameter values, based on our preliminary data and previously published studies. The power analyses revealed that a sample size of 100 subjects (50 per treatment group), even with 10% dropout, gives the study a >85% probability of detecting a 10-point group difference on a 0-100 rating scale (assuming a standard deviation of 16). Conventional metrics suggest that a 30% change, or difference score, is clinically meaningful, and this sample size would provide adequate power to detect a group difference of approximately 20%. Most of the analyses in the proposed study will involve delta scores reflecting changes within subjects, though the primary analysis of PGIC will compare raw scores rather than change scores (as the PGIC variable is a patient-reported rating of change). Scores of variables used in the secondary analyses should exhibit lower standard deviations than those assumed in the power calculations. We will examine the distribution of the delta scores between groups and will ascertain whether that distribution is normal. This information will allow us to determine whether parametric or nonparametric analyses should be used. Collectively, this sample size (n=100 total), together with our previously-observed very high retention rates and the substantial efficacy of the device, will provide more than adequate power to detect moderate-size effects.

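### Secondary outcomes are planned as change scores with no baseline covariate named, which can give up precision that a baseline-adjusted model would recover from the same data

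*Combined protocol and SAP*

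**What the plan says.** The Power Analyses section of the combined protocol and SAP gives the form of the analyses: "Most of the analyses in the proposed study will involve delta scores reflecting changes within subjects". The one exception named is the primary outcome, PGIC, which is itself a rating of change and is compared as a raw score. The same paragraph says that the distribution of the deltas will decide between parametric and nonparametric methods. It names no model and no covariate, and no other section does.

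The sentence does not list the outcomes it covers. The natural reading is the scales with a baseline value among the secondary outcomes in Research Objectives: "We will target the BPI, FIQR, PCS, PDI, HADS, healthcare utilization, and satisfaction questions as secondary outcome measures". That means BPI, FIQR, PCS, PDI and HADS. The satisfaction questions have no pre-treatment value.

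Three other statements bear on the point:

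- On secondary precision, Power Analyses says: "Scores of variables used in the secondary analyses should exhibit lower standard deviations than those assumed in the power calculations". It gives no value.
- There is an intermediate measurement: "All subjects will be asked to complete a packet of mailed mid-point assessments approximately 6 weeks after the start of the study". Its role in the analysis is not stated.
- Eligibility requires patients to "average 4 or greater on a pain intensity scale of 0 to 10", which may narrow the spread of baseline pain.

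**The concern.** Subtracting the baseline uses it, but with a slope fixed at 1. Where the true slope of follow-up on baseline is below 1, the subtraction over-corrects and adds baseline noise to the treatment comparison. Estimating the slope avoids this.

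Reduced pain is the first hypothesis in Research Objectives, yet the pain measure (BPI) is secondary and the power calculation covers PGIC only. With about 45 patients per arm completing, confidence intervals (CIs) for pain, function and mood may be wider than the data require. The only reassurance on secondary power is the remark about lower SDs, which depends on a correlation the plan does not state.

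The silence is also a prespecification gap. An unadjusted delta, a delta adjusted for baseline and an adjusted follow-up score would all fit the text, so the choice could be made after results are seen.

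**Working it through.** **Inputs from the plan (Power Analyses).** "These calculations assumed a two-tailed test and alpha level of 0.05"; "a sample size of 100 subjects (50 per treatment group), even with 10% dropout", so about 45 per arm; a 10-point difference; SD 16.

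**Inputs assumed.** Correlation r = 0.3, 0.5, 0.7. Ratio k = baseline SD / follow-up SD = 1, 0.9, 0.8. The plan gives neither.

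**Step 1: the plan's own figure.** For 10 points, SD 16 and 45 per arm, power is 84.2% (normal approximation) or 83.5% (noncentral t). With 50 per arm it is 87.8% or 87.2%. The stated figure of more than 85% is thus reproduced to within 2 points, though 45 per arm falls just short of it.

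**Step 2: variance ratio.** Set the follow-up variance to 1.

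- Variance of the delta: 1 + k² − 2rk
- Residual variance after baseline adjustment: 1 − r²
- Delta minus adjusted: (k − r)², which is never negative and is zero only when r = k (slope of 1)
- Ratio adjusted/delta: (1 − r²)/(1 + k² − 2rk), which is (1 + r)/2 at k = 1

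Example, r = 0.5: k = 1 gives 0.75/1.00 = 0.750; k = 0.8 gives 0.75/0.84 = 0.893.

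| k | r = 0.3 | r = 0.5 | r = 0.7 |
|---|---|---|---|
| 1 | 0.650 | 0.750 | 0.850 |
| 0.9 | 0.717 | 0.824 | 0.927 |
| 0.8 | 0.784 | 0.893 | 0.981 |

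**Step 3: cost of estimating the slope.** With N = 90 the variance is multiplied by about 1 + 1/(N − 4) = 1 + 1/86 = 1.0116. Net ratios are 0.658, 0.759, 0.860 (k = 1) and 0.794, 0.903, 0.992 (k = 0.8). Simulation with 20,000 trials per cell gave 0.654, 0.758, 0.862 and 0.806, 0.906, 0.992.

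**Step 4: equivalent sample size, before the slope cost.** 45 divided by the ratio: 45/0.650 ≈ 69, 45/0.750 = 60, 45/0.850 ≈ 53 per arm at k = 1; about 57, 50 and 46 at k = 0.8.

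**Step 5: illustrative power and CI width.** This borrows 10 points and SD 16 from the PGIC statement and reads 16 as the follow-up SD (noncentral t, 45 per arm). Adjusted figures omit the slope cost, which lowers them by at most about 0.4 points.

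| | r = 0.3 | r = 0.5 | r = 0.7 |
|---|---|---|---|
| Delta, k = 1 | 69.8% | 83.5% | 96.6% |
| Delta, k = 0.8 | 77.7% | 89.2% | 98.2% |
| Adjusted (any k) | 86.7% | 92.3% | 98.4% |

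At k = 1 the 95% CI half-width is 7.9, 6.7, 5.2 points for the delta and 6.4, 5.8, 4.8 adjusted. If 16 is instead the SD of the delta, delta power is 83.5% throughout; adjusted power is 95.3%, 92.3%, 88.9% (k = 1) or 91.1%, 87.3%, 84.1% (k = 0.8).

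**Step 6: the lower-SD remark.** Taking 16 as a single-time-point SD, a delta has a smaller SD only if 1 + k² − 2rk < 1, that is r > k/2: 0.50, 0.45 and 0.40 at k = 1, 0.9 and 0.8. Without r or a raw SD, the remark can be neither confirmed nor refuted.

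**The case against.** The strongest reply is that nothing in the plan is false. A delta comparison is valid under randomization, the quoted sentence does not exclude a covariate, and the primary analysis is untouched. All of that stands, and it is why this is a recommendation about efficiency and prespecification.

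A second reply is that the size is wholly assumed and can be nil. This also stands. At r = k = 0.8 the ratio is exactly 1, and the slope cost makes adjustment about 1% worse (1.012). Variance cuts also look larger than their effect on the interval: at r = 0.5 the net CI narrows by about 13% at k = 1 (√0.759 = 0.871) and 5% at k = 0.8 (√0.903 = 0.950).

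A third is that the gain is probably reduced for pain, the outcome that matters most here. The entry threshold may lower the baseline SD. Take r = 0.5, k = 1, keep the slope at 0.5, and cut the baseline SD to 0.8 of its value. The delta variance is then 0.75 + (1 − 0.5)² × 0.64 = 0.91, and the ratio is 0.75/0.91 = 0.824: an 18% cut instead of 25%. The gain is smaller but still useful.

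Finally, the formulas above are for linear models, while the plan keeps a nonparametric option. That calls for a conforming edit. It does not rescue the unadjusted delta, because a method chosen from the data is a further reason to name the model in advance.

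**Conclusion.** The concern holds, at the level of a change that should be made. For secondary scales with a baseline, an unadjusted delta can be less precise than a baseline-adjusted analysis of the same data. The net variance loss runs from about a third (r = 0.3, equal SDs) to about 1% (r = 0.7, k = 0.8): material at low to moderate correlation, negligible at high correlation with a narrower baseline. It rests on assumed r and k, about 45 completers per arm, and the reading that BPI, FIQR, PCS, PDI and HADS are the outcomes analysed as deltas. There is no bias, and the PGIC sample size is unaffected. The remark about lower secondary SDs is unsupported, not shown wrong. Confidence is medium, because the size cannot be fixed from the documents.

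**What to change.** Add to the analysis plan before unblinding:

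> For each secondary outcome with a baseline value, the 3-month score will be modelled on treatment plus that measure's baseline value, and the adjusted difference reported with its 95% CI.

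- A repeated-measures model that also uses the 6-week packet is an acceptable alternative. Name one of the two as the main analysis.
- If the delta is kept as the reported scale, add baseline as a covariate; the treatment estimate is then identical.
- Amend the sentence on parametric versus nonparametric methods to match, for example by keeping a rank-based test as a sensitivity analysis.
- Qualify the remark on lower SDs by stating the raw SD and correlation it assumes.
- A covariate for PGIC is optional. At 10 points, SD 16 and 45 per arm, a covariate with an assumed correlation of 0.1 gains nothing once the slope cost is counted; at 0.3 it adds about 2.9 points of power.

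The cost is wording only: the deltas already require the baseline scores, so no data, visits or change in sample size are needed.

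### Change-score tests, chosen after an undefined normality look, should give way to baseline-adjusted ANCOVA for the secondary scales, and the primary PGIC test should be named

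*Combined protocol and SAP*

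**What the plan says.** The Research Objectives paragraph fixes the primary outcome: "We will target the PGIC as the primary outcome measure". It lists the BPI, FIQR, PCS, PDI, HADS, healthcare utilization and satisfaction questions as secondary.

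The Power Analyses section says that most analyses will use within-subject change, with the primary as an exception: "the primary analysis of PGIC will compare raw scores rather than change scores". The only rule for choosing a test follows: "We will examine the distribution of the delta scores between groups and will ascertain whether that distribution is normal", and then "This information will allow us to determine whether parametric or nonparametric analyses should be used".

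For power, "These calculations assumed a two-tailed test and alpha level of 0.05". The claim is that "a sample size of 100 subjects (50 per treatment group), even with 10% dropout" gives a ">85% probability of detecting a 10-point group difference on a 0-100 rating scale", "assuming a standard deviation of 16". No test is named for the PGIC anywhere in the document, and no power is given for a nonparametric test.

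**The concern.** Three things need attention.

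- **Secondary scales.** Where a change score can be formed, a baseline score exists. Subtracting it is a valid way to use it in a randomized trial, but generally less precise than adjusting for it.
- **The selection rule.** It depends on trial data, sets no criterion for normality and names neither candidate test. The two routes also answer different questions: a difference in means or a shift in ranks.
- **The primary outcome.** The rule concerns change scores, and the PGIC has none, so the primary test is left open.

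At stake are precision on the main secondary scales, and a primary p-value and effect measure that could be settled after the outcomes are seen.

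**Working it through.** **1. The plan's own power figure.** Inputs from the Power Analyses section: difference 10, SD 16, two-sided alpha 0.05, 50 per arm, 10% dropout. So d = 10/16 = 0.625, and completers are 50 × 0.9 = 45 per arm.

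Normal approximation: power = Φ(d·√(n/2) − 1.96).
- n = 50: Φ(3.125 − 1.96) = 87.8%; noncentral t, 87.2%.
- n = 45: Φ(2.965 − 1.96) = 84.3%; noncentral t, 83.5%.

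The stated figure is reproduced to within 2 points. Strictly, more than 85% is met before dropout and just missed after it.

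**2. The rank test.** For normal data its efficiency relative to the t-test is 3/π = 0.955, so 45 per arm acts like 45 × 0.955 = 43.0. Power is 81.7% (noncentral t) or 82.6% (normal approximation); direct simulation with 20,000 runs gave 81.4%. The choice of test therefore costs about 83.5 − 81.7 = 1.8 points.

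The document gives no outcome distribution, so other shapes are assumptions. Simulated rank-test power at 45 per arm, same shift and SD:

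| Shape | Rank-test power |
|---|---|
| Uniform | 77.9% |
| Laplace | 92.7% |
| Lognormal (sigma 0.5) | 94.5% |
| t, 3 df | 97.5% |
| Exponential | 97.7% |

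**3. Type I error if normality decides.** With Shapiro-Wilk at 0.05 in each arm, then the t-test or the rank test (45 per arm, 4,000 runs per shape), rejection under the null was 5.1% (normal), 5.2% (t, 3 df) and 4.8% (exponential). A separate simulation of a normality gate (50 per arm, five shapes, 8,000 trials each) gave 4.7–5.3%.

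**4. Change score against ANCOVA.** Let baseline and 3-month scores share variance σ² and correlate at r within arm. Per subject:
- change score: σ² + σ² − 2rσ² = 2σ²(1 − r)
- ANCOVA residual: σ²(1 − r²)
- ratio: (1 − r²) / [2(1 − r)] = (1 + r)/2

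At r = 0.5 the ratio is 0.75 (25% less variance). At r = 0.7 it is 0.85 (15% less). The document gives no r, so both values are assumed. The ratio is below 1 whenever r is below 1, apart from the negligible cost of estimating one slope.

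**The case against.** The best defence is that little here is an error. Change-score analysis is unbiased under randomization, the missing PGIC test is largely a missing detail, and a normality gate holds its level. Much of that stands, and it rules out several stronger readings.

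- **Inflated type I error.** A reader might infer this from the data-driven choice. Taking the smaller of the two p-values does reject 5.6–7.5% of the time in simulation (50 per arm), but the plan does not describe that procedure. It says normality decides.
- **Power fails on the nonparametric route.** The t-test is also below 85% at 45 per arm. The 81.7% applies to normal data, for which the rule would normally keep the parametric test. For skewed or heavy-tailed shapes the rank test is well above 85%; for light-tailed shapes it is lower.
- **The shortfall depends on the dropout assumed.** The design text elsewhere expects 15% dropout and recruits 115. That leaves 115 × 0.85 / 2 = 48.9 per arm and t-test power of 86.4%.
- **An unblinded look.** The text says the distributions are examined between groups. It does not say that treatment labels are revealed, and a look by coded group is compatible with the Blinding section.
- **Precision lost on every secondary outcome.** Only most analyses use change scores, and satisfaction with the device has no evident baseline before its use.

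The defence does not remove the efficiency point, because ANCOVA uses the same data at no extra burden. Nor does it supply a test for the PGIC.

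**Conclusion.** The point holds in limited form and should be acted on; it does not call the trial's validity into question. As written, the plan uses a less precise analysis for the scale-based secondaries and a selection rule with no criterion, and it names no test for its primary outcome.

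The measurable gain is a 15–25% lower variance for r between 0.7 and 0.5, assuming equal variances at the two times. It applies only to scales with a baseline score.

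For the PGIC, the defect is lack of prespecification. Neither type I error inflation nor a power loss peculiar to the rank test is demonstrated. At the plan's 10% dropout both tests fall slightly short of the stated power under normality, and most of the rank test's gap from the 87.2% available at 50 per arm comes from dropout (87.2 to 83.5) rather than from the test (83.5 to 81.7).

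**What to change.** 1. For BPI, FIQR, PCS, PDI and HADS, replace the change-score tests with ANCOVA of the 3-month score on arm and baseline score.
2. Delete the normality-based choice between parametric and nonparametric analyses.
3. Before unblinding, name one test of the raw 3-month PGIC score as primary (t-test or Wilcoxon rank-sum), with the other as a stated sensitivity analysis.
4. Restate power for the named test at 45 per arm: about 83% for the t-test or about 82% for the rank test under normality. State the PGIC response scale as well, which the text does not give. If it has seven categories (an assumption), cutting a normal 0–100 variable into seven levels gave simulated power of about 80% (t-test) and 79% (rank test) at 45 per arm.

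The cost is a few sentences in the analysis plan. Visits, data collection and sample size need not change; the only other consequence is a slightly lower stated power figure.
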